#### **10.2 Procedures for accounting for missing, unanalyzable and questionable data**

In case of missing, unanalyzable and questionable data appropriate statistical methods will be applied. Patients who did not complete the planned treatment course will be added to the analysis by the last observation carried forward method.

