### 3.4 Schedule of the study procedures

Prior to the study enrollment, examination to assess conformity with the inclusion/exclusion criteria, to obtain baseline data and ensure washout period (if necessary) will be carried out for a patient. After enrollment and initiation of the investigated treatment, the study procedures will be conducted to assess product tolerability, safety, efficacy and patient compliance. All scheduled visits are mandatory. Washout period will be carried out only for patients with prior antihypertensive therapy. Each patient is to sign the informed consent prior to any study activities including screening / “examination to assess conformity with the in- and exclusion criteria.

Schedule of the study procedures is presented in Table 2.

	Visit 0 Screening	Visit 1	Visit 2	Visit 3	Visit 4
	Day-14...-1	Day 0	Week 8	Week 24	Week 48
Drug administration		+	+	+	+
Dose titration / treatment adjustment		+	+	+	
BP / HBR / Patients' diary analysis	+	+	+	+	+
ECG, K, Na	+			+	
Creatinine	+			+	
ALT/AST	+			+	
Parathyroid hormone	+				
X-ray densitometry, BMD	+				+
Total calcium, Phosphorus	+			+	+
PWV		+			+
IMT + evaluation of subclinical atherosclerosis		+			+
Telomerase activity		+			+
Osteocalcin		+		+	+
Collagen type 1 C-telopeptide		+		+	+
Osteoprotegerin, RANKL		+			+
Safety Information	+	+	+	+	+

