### 3.5 Number of patients:

114 patients will be enrolled to the study to ensure the final sample size. The patients will be randomized to one of two treatment groups (moxonidine group or bisoprolol group) using simple

randomization envelopes. It is anticipated that a screening of 300 subjects will be needed in order to enroll the minimum of 100 patients to the study.

According to the study protocol, patients randomization to the control and investigated groups will be carried out randomly and, therefore, it is assumed that the control and the investigated groups will be matched by the basic measured parameters; the number of subjects in the main and control groups is planned to be equal.

The study endpoints are measured prior to the studied product initiation (V1) and after completion of 48-week treatment with the investigated product (V4).

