#### **4.6 Early withdrawal procedures**

All patients who were withdrawn from the study early are asked to complete the final visit procedures, if possible. If the decision to terminate the patient participation was made between two scheduled visits, the patient is asked to come for the upcoming scheduled visit, as usual, or make an unscheduled visit.

The reason for the early withdrawal should be indicated in the source documents. If the patient is lost to follow-up, the investigator should make all reasonable efforts to contact the

patient to obtain information on date of withdrawal and reason for the investigated product discontinuation. If the patient cannot be reached, she will be considered as lost to follow-up.

In the case of early investigated product discontinuation due to an adverse event (regardless of whether the event should be immediately reported), the researcher must make every effort to collect information regarding the AE outcome. This information is added to the source documents and CRF, under adverse events section.

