#### **Patient population for statistical analysis**

The following patient populations will be used for the statistical analysis:

**Intention-to-treat population (ITT):** all enrolled patients with investigations data from visits V3 or V4, excluding the enrollment visit.

**Per protocol patient population (PP):** patients who completed the study according to the protocol.

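### The LOCF rule in section 10.2 conflicts with the per-protocol efficacy set and, wherever it is applied, enters a change of exactly zero for BMD, PWV, IMT and telomerase and can count a withdrawn woman as a week-48 BP responder

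*Combined protocol and SAP*

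**What the plan says.** Section 10.2 gives one rule for non-completers: "Patients who did not complete the planned treatment course will be added to the analysis by the last observation carried forward method". It exempts no endpoint and names no sensitivity analysis.

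The subsection on analysis populations defines ITT as "all enrolled patients with investigations data from visits V3 or V4, excluding the enrollment visit", and PP as the women who finished the study as the protocol requires. Sections 6 and 10.3 both place the efficacy analysis in PP. No efficacy analysis is assigned to ITT.

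Measurement times in the section 3.4 schedule:
- "X-ray densitometry, BMD": screening and V4 only.
- PWV, "IMT + evaluation of subclinical atherosclerosis" and "Telomerase activity": V1 and V4 only.
- "Osteoprotegerin, RANKL": V1 and V4. The laboratory table in section 3.7 agrees, but the V3 visit text in section 3.6.5 also lists OPG and RANKL.
- Osteocalcin and CTX: V1, V3 and V4.

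Section 10.3 defines BP response as a value below 140/90 mmHg at the visit, assessed at V2, V3 and V4. It sets no on-treatment condition and no rule for withdrawn women. Under sections 4.5 and 5.3, leaving the study and stopping treatment go together, and reason 6 in section 4.5 covers a renewed BP rise once target had been reached. On early withdrawal, section 4.6 says: "All patients who were withdrawn from the study early are asked to complete the final visit procedures, if possible".

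**The concern.** LOCF needs an informative last value. For an endpoint measured only at baseline and week 48, the last value of a woman with no final measurement is her baseline. Carrying it forward asserts that nothing happened to her in 48 weeks. Those zeros pull each arm's mean change towards zero and usually reduce the SD. If more women are carried in one arm than in the other, which is possible in an open-label trial, the zeros also create a difference between arms that does not exist.

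For BP the error is one of classification. A woman at target at V3 and then withdrawn, even for loss of BP control, can be reported as controlled at week 48 on a treatment she no longer takes. Section 10.1 says the primary result will be presented as the number and proportion at target BP at V4, so that figure may be prominent.

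The conflict over analysis sets matters too. A reader cannot tell from the plan whether non-completers enter the efficacy results at all.

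**Working it through.** **Step 1: which rule reaches whom.** PP contains completers and LOCF applies to non-completers, so in the stated efficacy set LOCF has essentially nothing to fill. Yet section 10.2 says non-completers are added to the analysis. Both cannot describe the same efficacy analysis. LOCF can act in ITT, but ITT requires V3 or V4 data, so women lost before V3 are outside it. The carried women are those with V3 data and neither a V4 nor an early-final value.

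**Step 2: what is carried for such a woman.**

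| Endpoint | Last value | Change entered for V4 |
|---|---|---|
| BMD | screening | exactly 0 |
| PWV, IMT, telomerase | V1 | exactly 0 |
| RANKL | V1 under sections 3.4 and 3.7; V3 under section 3.6.5 | 0, or the week-24 change |
| CTX, osteocalcin | V3 | week-24 change labelled week 48 |
| BP response | V3 | V3 status |

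**Step 3: effect on mean and SD.** Inputs from the plan: 57 per arm (section 3.2) and two-sided 0.05 (section 10.1). The plan gives no effect size, SD, power or drop-out rate, so it has no figure of its own to reproduce. Assumptions: change SD = 1; a fraction f of the analysed women carried at zero; carrying unrelated to the true change. For a true mean change μ:

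- mean after LOCF = (1 − f)μ
- variance after LOCF = (1 − f) + f(1 − f)μ²

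With equal f in both arms, a true difference in mean change keeps 95%, 90%, 85%, 80% and 70% of its size at f = 5%, 10%, 15%, 20% and 30%. When μ is near zero the SD falls to √(1 − f) = 0.97, 0.95, 0.92, 0.89 and 0.84 of its true value. A numerical check at f = 15% with μ near −0.5 gave a mean change of −0.427 instead of −0.503 and an SD of 0.937 instead of 0.997. The largest imputed change was 0.0.

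**Step 4: false difference.** With no true difference, a common change μ and carried fractions of 20% and 10%:

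- false difference = μ × (0.20 − 0.10)
- SE = √[(v₁ + v₂)/57], with v₁ and v₂ from the variance formula
- type I error = Φ(q − 1.96) + Φ(−q − 1.96), with q = false difference / SE

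| μ (SD) | v₁, v₂ | SE | False difference (SD) | Type I error |
|---|---|---|---|---|
| 0.25 | 0.810, 0.906 | 0.173 | 0.025 | 5.2% |
| 0.5 | 0.840, 0.923 | 0.176 | 0.05 | 5.9% |
| 1 | 0.960, 0.990 | 0.185 | 0.10 | 8.4% |

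Simulation of 20,000 trials gave 8.3% for the last row.

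**Step 5: power.** Take a true difference of 0.50 SD, with mean changes 0.50 and 0. With everyone observed, power = Φ(0.50/√(2/57) − 1.96) = 76%. LOCF uses difference 0.50(1 − f) and the variance above. A completers-only analysis uses 57(1 − f) per arm.

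| f | LOCF | Completers only |
|---|---|---|
| 10% | 71.1% | 71.6% |
| 15% | 68.4% | 69.2% |
| 20% | 65.5% | 66.5% |

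LOCF itself costs about 0.5 to 1 point. The rest is lost to drop-out under either method.

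**Step 6: BP.** Points credited at V4 = f × the proportion of carried women at target at V3. With f = 15% and 60% at target (both assumed), 0.15 × 0.60 = 9 points, or 0.09 × 57 ≈ 5 women per arm. Across f = 5% to 30% and 40% to 80% at target, the range is 2 to 24 points.

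**The case against.** The strongest reply is that the planned efficacy analysis is PP, so LOCF may never touch a reported efficacy result. ITT drops women without V3 or V4 data. The words about the enrollment visit in its definition might also be read as barring V1 values from being carried, which would leave PWV, IMT and telomerase missing rather than zero. Section 4.6 asks withdrawn women for final-visit procedures, or to attend the next scheduled or an unscheduled visit, so some real values will exist. The study is explorative, the primary endpoint CTX has a V3 value, and details are deferred to a later SAP.

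Much of this stands, and it rules out several stronger readings that a reader might infer:
- **Zeros enter whichever set is used.** Not supported: PP is the stated efficacy set.
- **RANKL always gets a zero.** Not supported: section 3.6.5 lists it at V3.
- **The primary endpoint gets a carried baseline.** Not supported for a woman with V3 CTX: her week-24 value is carried.
- **LOCF causes the fall in power.** Not supported: a completers-only analysis loses nearly as much.
- **A type I error of 8% is to be expected.** It needs a common change of 1 SD, for which the documents give no basis. At 0.25 or 0.5 SD it is about 5% or 6%.

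The reply does not rescue the rule. Section 10.2 says non-completers are added, and the populations text says ITT will be used. The phrase on the enrollment visit is ambiguous, and the BMD baseline is taken at screening. The early final visit is requested only where possible, and its values are not week-48 values.

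**Conclusion.** The concern holds in conditional form. Section 10.2 conflicts with sections 6 and 10.3 on whether non-completers enter the efficacy analysis. Any analysis that follows section 10.2 literally enters exact zeros for BMD, PWV, IMT and telomerase, relabels week-24 CTX and osteocalcin as week 48, and can credit BP response at V4 to women already withdrawn.

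The harm is bias, and in most cases an understated SD: differences shrink to (1 − f) of their size, and unequal carrying creates false differences. At 20% against 10% carried these are 0.025 to 0.10 SD for common changes of 0.25 to 1 SD. All carried fractions, common changes and BP control rates here are assumptions. Carried fractions are not drop-out rates either, because early leavers fall outside ITT and some withdrawn women will have a final measurement. The plan should be changed, but nothing here shows that the planned PP result for CTX is distorted by LOCF.

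**What to change.** 1. Delete LOCF from section 10.2 and state which analysis set each efficacy analysis uses, so that sections 6, 10.2 and 10.3 agree.
2. For CTX and osteocalcin, fit a repeated-measures model to V3 and V4 with baseline, arm, visit and arm-by-visit, and report the V4 contrast. The V3 samples are already scheduled.
3. For endpoints measured only at baseline and V4, use a baseline-adjusted analysis of observed V4 values, with multiple imputation as sensitivity. Never carry the baseline forward.
4. Reconcile RANKL sampling between sections 3.4, 3.7 and 3.6.5. Its analysis under item 2 or 3 follows from the answer.
5. For BP response, count women who are withdrawn or have no value at the visit as non-responders. This is itself a single imputation, so add an observed-data or multiple-imputation sensitivity analysis.

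The cost is SAP wording and slightly more programming, with no added visits or samples. Section 10.1 leaves the SAP open until data lock.

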#### **Patient population for statistical analysis**

The following patient populations will be used for the statistical analysis:

**Intention-to-treat population (ITT):** all enrolled patients with investigations data from visits V3 or V4, excluding the enrollment visit.

**Per protocol patient population (PP):** patients who completed the study according to the protocol.

**Analysis of demographics, disease data, concomitant therapy, and other baseline data**

Demographic data (age, gender), the initial condition data (height, weight, body mass index) will be presented along with a summary in the form of a rate or percentage, or by using the mean, standard deviation, median, interquartile range, minimum and maximum, depending on the type of the variable.

**10.3 Efficacy Analysis**

Efficiency analysis will be carried out in the population of patients who completed the study according to the protocol (PP).

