#### **4.5 Study withdrawal criteria**

A patient may be withdrawn from the study before the treatment is started, if the investigator discovers deviations from any inclusion criteria, exclusion criteria, or criteria for the treatment initiation. Patients who withdrew before the treatment start (i.e., during screening or washout period), will be substituted with new patients.

In the present study, withdrawal from the study will also mean discontinuation of the investigated treatment.

The patient may be withdrawn from the study due to the following reasons:

1. Withdrawal of the informed consent to participate in the study.
2. Low treatment compliance (<80%).
3. Adverse events that in the investigator's opinion make the treatment continuation impossible, dangerous, or inconsistent with best patient interest and safety. A SAE is not necessarily the cause of early patient withdrawal from the study.
4. According to the investigator, continued participation of the patient in the study threatens the patient's safety.
5. It is necessary to administer treatment prohibited by the study protocol.
6. Failure of the investigated treatment (i.e., recurrent rise of blood pressure  $\geq 180/120$  mmHg after previously achieved target BP level).
7. Death of the patient.
8. Sponsor decision.

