**At visit V2:**

- If a patient responds to the selected treatment regimen (BP <180/120 mmHg), the investigator will continue this regimen until the next visit.
- If a patient does not respond to the selected treatment regimen (BP  $\geq$ 180 /120 mmHg), the patient is withdrawn from the study.

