**5.3 Investigated treatment withdrawal**

If the investigated treatment should be withdrawn for any reason before the end of the study, gradual investigated products doses reduction is not required. The early treatment withdrawal means the patient is withdrawn from the study.

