## **6 EFFICACY EVALUATION**

Efficiency analysis will be carried out in the population of patients who completed the study according to the protocol.

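### Completer-only efficacy analysis conflicts with the LOCF rule and a restricted ITT set, so the CTX comparison and the responder denominator are either selected after randomisation or undefined

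*Combined protocol and SAP*

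**What the plan says.** Three statements govern who enters the efficacy analysis.

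- **Sections 6 and 10.3** name protocol completers. Section 6: "Efficiency analysis will be carried out in the population of patients who completed the study according to the protocol". Section 10.3 repeats this with the set's label added, "Efficiency analysis will be carried out in the population of patients who completed the study according to the protocol (PP", and lists the primary and secondary indicators beneath it.
- **Section 10.2, missing data:** "Patients who did not complete the planned treatment course will be added to the analysis by the last observation carried forward method". Neither the analysis nor the population is identified.
- **Patient population for statistical analysis** (after 10.2) defines ITT as "all enrolled patients with investigations data from visits V3 or V4, excluding the enrollment visit". It says in general terms that both sets will be used, but assigns ITT to no endpoint.

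Other sections decide who completes. Under Section 5.1, at V2 and again at V3, the rule beginning "If a patient does not respond to the selected treatment regimen" withdraws a patient whose BP is ≥180/120 mmHg. Section 5.3 adds: "The early treatment withdrawal means the patient is withdrawn from the study". Section 4.5 states the converse: "In the present study, withdrawal from the study will also mean discontinuation of the investigated treatment". Section 4.6 still seeks closing data: "All patients who were withdrawn from the study early are asked to complete the final visit procedures, if possible".

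Section 10.3 defines a responder as BP below 140/90 mmHg at the visit. It gives no rule for patients who have already left.

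**The concern.** Completion is decided after randomisation. In an open-label trial the assignment is known to both patient and investigator when adverse events, compliance, prohibited medication or BP lead to withdrawal. A completer comparison is therefore no longer protected by randomisation. It also discards data already recorded: the V2 and V3 blood pressures, and the V3 CTX, of anyone who leaves before V4.

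The LOCF sentence cannot operate inside a set that contains only completers. Either it applies to some other, unnamed analysis, or it contradicts Sections 6 and 10.3. The analyst must choose, and Section 10.1 requires the detailed SAP only before the data lock point, when results by arm may already be visible in an open-label trial. What is at stake is the primary between-group comparison of CTX and the proportion of patients at target BP.

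**Working it through.** There is no figure of the plan's own to reproduce. Section 10.5 says that no formal sample size calculation was made, and no dropout or withdrawal rate is given. From the documents come 57 patients per arm (Section 3.2), the visit schedule (Section 3.4) and the responder definition (Section 10.3). All withdrawal counts, exclusion fractions and outcome gaps below are assumptions.

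**Step 1. One patient under the three rules.** Take a patient withdrawn with an observed BP ≥180/120 mmHg.

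| Withdrawn at | PP (10.3) | LOCF (10.2) | ITT set as defined |
|---|---|---|---|
| V2, no final visit | not counted at any visit | not at target at V2, V3, V4 | excluded |
| V3, no final visit | not counted at any visit | not at target at V3, V4 | included |

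If she attends the early closing visit, the result depends on how that visit is coded. Sections 3.6.6 and 5.1 call the final visit V4, but the coding of an early one is not stated.

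**Step 2. Responder rate under PP.** Assume 34 of 57 truly at target in each arm (59.6%), and w patients withdrawn for BP failure, none of them at target. The PP rate is 34/(57 − w).

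| Withdrawn (arm A v arm B) | PP rates | False difference (points) |
|---|---|---|
| 0 v 0 | 34/57 = 59.6% in both | 0 |
| 1 v 0 | 34/56 = 60.7% v 34/57 = 59.6% | +1.1 |
| 3 v 1 | 34/54 = 63.0% v 34/56 = 60.7% | +2.2 |
| 9 v 3 | 34/48 = 70.8% v 34/54 = 63.0% | +7.9 |
| 6 v 6 | 34/51 = 66.7% in both | 0, but each arm reads 7.0 too high |

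Differences are taken before rounding. The arm with more failures looks better. Counting these patients as not at target restores 34/57 v 34/57 in every row.

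**Step 3. Withdrawals for other reasons.** Suppose the 9 v 3 left for reasons unrelated to BP and all were at target. PP gives 25/48 = 52.1% v 31/54 = 57.4%, or −5.3 points. Scoring them all as not at target gives 25/57 = 43.9% v 31/57 = 54.4%, or −10.5 points. A blanket failure rule can therefore do more harm than PP.

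**Step 4. CTX in completers.** Let p be the fraction excluded in an arm and d the mean outcome gap between excluded patients and completers. The arm's full mean equals the completer mean plus p × d, so the absolute completer bias in the difference is |p1 × d1 − p2 × d2|. Take p from 0 to 30% and d from 0 to 1 SD, in the same direction in both arms:

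- p × d equal in both arms: 0
- 20% v 10% excluded, gap 0.5 SD in both: 0.10 − 0.05 = 0.05 SD
- 30% v 10% excluded, gap 1 SD in both: 0.30 − 0.10 = 0.20 SD
- 30% v 10% excluded, gaps 1 v 0 SD: 0.30 − 0 = 0.30 SD
- 30% in both arms, gaps 1 v 0 SD: 0.30 − 0 = 0.30 SD

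The last case shows that equal exclusion rates are no safeguard if the kind of patient excluded differs.

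**Step 5. LOCF on continuous endpoints.** By the schedule, BMD, PWV, IMT and telomerase have no value between baseline and V4. Without final-visit data, LOCF carries baseline forward and scores zero change, as it does for CTX lost before V3. If a fraction p is affected and would otherwise have changed like the rest, the mean change is multiplied by (1 − p); for p of 0–30% it shrinks by 0–30%. RANKL is left out here because Section 3.6.5 adds a V3 sample that Section 3.4 and the laboratory table do not.

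**The case against.** A reader might infer that BP failures definitely vanish from the denominator and that the ITT set has no efficacy role. The documents do not go that far. The loss follows from Section 10.3, but the LOCF sentence in 10.2 would carry a failing reading forward and score the patient as not at target. The population section says both sets will be used, and safety has its own set, so ITT was probably meant for efficacy. This part of the objection stands: the defect is an unresolved conflict, not a settled exclusion.

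It also stands that the BP withdrawal trigger is unsettled. Sections 3.6.4 and 3.6.5 titrate when target is missed. Section 5.1 withdraws at ≥180/120 mmHg. Section 4.5 says a patient may be withdrawn, and its failure criterion needs a recurrent rise after target was reached. How many patients the BP example describes is therefore uncertain. Baseline BP ≥180/110 mmHg is excluded, and dose increase and add-on therapy are available, so failures may be few.

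The remaining argument is that the trial is explorative, its results are descriptive and details are left to a SAP. That does not remove the defect. The primary endpoint is a between-group comparison, Section 10.1 specifies two-sided tests at 0.05, and a descriptive completer rate carries the same bias. Section 10.3 also reads results against historical control, so inflation common to both arms matters. The protocol itself fixes PP in two sections and contradicts it in a third. Target BP is only the last of seven secondary endpoints, but the conflict over the analysis set applies equally to CTX.

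**Conclusion.** Wrong as written. Followed literally, the plan yields either a comparison selected after randomisation or one whose population is undefined, for the primary endpoint as well as the responder proportion. That conclusion rests on the text alone.

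The sizes rest on assumptions. For BP, the false difference is 0 to 7.9 points over the failure counts shown, given 34/57 truly controlled in each arm; the upper end needs 9 v 3 failures, and 1 v 0 or 3 v 1 gives only 1 to 2 points.

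A reader might also infer that the CTX result will be biased by a known amount or towards a particular arm. The documents support neither. Bias is zero when the product of exclusion fraction and outcome gap is the same in both arms, and its direction is unknown. The figure of 0 to 0.30 SD is a range over assumed inputs, not an estimate. Nor does the argument justify scoring every withdrawal as a BP failure, as Step 3 shows.

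**What to change.** - **Sections 6 and 10.3:** make all randomised patients, analysed as assigned, the primary efficacy set, with PP supportive. Drop the V3/V4-data condition from the ITT definition.
- **Section 10.2, continuous endpoints:** replace LOCF with a baseline-adjusted analysis of all available data, using V3 and V4 for CTX and osteocalcin with the V4 contrast as the endpoint, plus one prespecified missing-data sensitivity analysis. Patients with no final value for BMD, PWV, IMT or telomerase enter only through that sensitivity analysis.
- **Early final visits (Section 4.6):** include these data at their actual date, not relabelled as week 48.
- **Responder proportion:** count a patient withdrawn with an observed BP ≥180/120 mmHg as not at target at that visit and later ones. For other withdrawals, prespecify one rule and show the result under the alternative.
- **Reconciliation by the sponsor:** Sections 3.6.4, 3.6.5, 4.5 and 5.1 (V2 and V3) must agree on when BP leads to withdrawal. No clinical rule is proposed here.

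The analysis changes cost wording only. No new visit or test is needed, because closing data are already requested and CTX and osteocalcin are already measured at V3. The downside is that estimates will include patients who are off treatment or on prohibited medication, some of which Section 5.4.2 says affects bone metabolism. This may move the effect in either direction, and the supportive PP analysis will show by how much the two differ.
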